	
gefitinib, afatinib) will be enrolled across the enrollment phases.
 
The sample size considerations are based on the probability of observing PPA/NPA estimates in the desired range as well as the size of the confidence intervals around these estimates. The results of the central tissue assessments will be used in analysis where available. In patients without central CLIA laboratory results, local assessments of genomic alterations in tissue will be utilized. We anticipate that ~20% of samples may be excluded from analysis due to insufficient DNA yield and/or pre-specified QC criteria.

Clinical Sites	Approximately 25 USA and International centers including centers in France, Germany, Ireland, Spain, United Kingdom, Japan, Chile and Mexico.
Inclusion/Exclusion Criteria	
Initially, approximately 200 patients will be enrolled regardless of genomic alteration status in tumor tissue (First Enrollment Phase). This will be followed by a Second Enrollment Phase including approximately 39 patients with clinically relevant alterations in EGFR and approximately 21 patients with alterations in ALK (EML4-ALK fusions) (as assessed in tumor tissue). In addition, approximately 50 patients progressing on erlotinib, gefitinib, or afatinib will be included across the enrollment phases (see Section 4, Figure 1).
 
Inclusion Criteria (all of the below)
 
 • Patients must be 18 years or older. • Patients with stage IV non squamous NSCLC who are either newly diagnosed or progressing on any treatment (progression defined as increasing tumor size or new metastatic lesions on clinical or imaging assessment). Patients with available tissue sample from a metastatic site or, if the patient presents with stage IV disease at diagnosis, from the primary tumor or a metastatic site. If a patient is progressing on EGFR targeted therapy (erlotinib, gefitinib, afatinib), tumor tissue sample is required only if available. • No new systemic anti-tumor therapy administered in the interval between the tissue biopsy and collection of the blood sample (interval not to exceed eight weeks). Local radiation therapy is permitted.

CONFIDENTIAL – PROPRIETARY PROPERTY OF GENOMIC HEALTH, INC.

	<h2>Study Protocol</h2>
---	-------------------------

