4. STUDY DESIGN

This is a prospective clinical study to characterize the concordance of key clinically relevant genomic alterations in tumor tissue (biopsy/excision/cytology) and liquid biopsy (blood) using the Genomic Health LBMP in patients with stage IV non squamous NSCLC, that are either newly diagnosed with metastatic disease or progressing on therapy (any line). Tissue biopsy and blood collection (liquid biopsy) should be less than eight weeks apart and with no new systemic antitumoral treatment given in the interval between the tissue biopsy and blood collection. Local assessment of tumor tissue samples will be performed at each participating institution as per their clinical standard of care practices and results from the local assessment of genomic alteration status will be used.

Additionally, detection of *EGFR* T790M alterations in plasma samples will be characterized in patients progressing on EGFR targeted therapy (erlotinib, gefinitib, afatinib).

The study will enroll a total of approximately 310 patients (Figure 1):

- approximately 260 patients with plasma and tissue samples will be enrolled. Initially, approximately 200 patients will be enrolled (First Enrollment Phase) regardless of genomic alteration status in tumor tissue. In order to enroll approximately 69 patients with alterations in *EGFR* and 31 patients with alterations in *ALK* this First Enrollment

CONFIDENTIAL – PROPRIETARY PROPERTY OF GENOMIC HEALTH, INC.

Study Protocol

Phase will be followed by enrollment of patients in a with genomic alterations in *EGFR* and *ALK* (Second Enrollment Phase) as described in Table 2. Patients in both enrollment phases may be either newly diagnosed or progressing on therapy.

- approximately 50 patients with plasma samples (concurrent tumor tissue sample not mandatory) who are progressing on EGFR targeted therapy (erlotinib, gefitinib, afatinib) will be enrolled across the enrollment phases. We expect that approximately 25 of these patients will have T790M alteration.

We anticipate that ~20% of samples may be excluded from analysis due to insufficient DNA yield and/or pre-specified QC criteria.

Table 2: Patient enrollment targets for patients with plasma and tissue samples

[figure not shown]
	All patients	Patients with EGFR alterations*	Patients with ALK alterations*	Patients without EGFR or ALK alterations*

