First Enrollment Phase: Approximate number of patients enrolled regardless of presence or absence of genomic alterations	200	30	10	160
Second Enrollment Phase: Approximate number of patients enrolled based on known gene alterations of interest	60	39	21	NA
Total	260	69	31	160

*Expected prevalence: 15% for *EGFR* alterations, 5% for *ALK* alterations, 80% without *EGFR* or *ALK* as these alterations are expected to be mutually exclusive.

CONFIDENTIAL – PROPRIETARY PROPERTY OF GENOMIC HEALTH, INC.

Figure 1. Schematic view of the patient categories to be included in the study

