4.1 Required Procedures at Clinical Sites

Participants who are eligible and consent to participate in the study will provide a venous blood sample (2X 10 mL Streck tubes) at a single study related visit. Participants will have no further visits as part of this study. Participants data will be collected at time of progression or at 12 months after blood sample collection, whichever occurs first and in addition, data will be collected to permit outcome analysis of the interim analysis. Participation in the study will not alter clinical care. All other clinical procedures performed and collection of non-study data will be in accordance with each participating institution’s standard of care. Local assessment of tumor tissue samples will be performed at each participating institution as per their clinical standard of care practices and results from the local assessment of genomic alteration status will be used. Each site will need to provide a single H&E slide to Genomic Health for an independent pathology review.

CONFIDENTIAL – PROPRIETARY PROPERTY OF GENOMIC HEALTH, INC.

	<h2>Study Protocol</h2>
---	-------------------------

Table 3. Requirements by patient category to help identify correct patients and required materials at the single required patient visit. Detailed overview in Table 6 (page 39).

Requirements	Patient Category (see Figure 1)		
	A: Newly diagnosed with stage IV disease	A: Patient progressing on treatment (except if progressing on erlotinib, gefitinib, or afatinib)	B: Patient progressing on erlotinib, gefitinib, or afatinib
Biopsy/cytology/excision performed on primary or metastatic lesion	X		
Biopsy/cytology/excision performed on metastatic lesion		X	Only if available
Local pathology report	X	X	X (original diagnosis)
Local mutation report	X	X	X (original diagnosis)
Provide H&E slide from biopsy/cytology/excision to Genomic Health for independent review	X	X	X
Blood sample (2X 10 mL) collected in Streck tubes	X Prior to initiating new systemic anti-tumor treatment AND no more than 8 weeks after tissue biopsy	X Prior to initiating new systemic anti-tumor treatment AND no more than 8 weeks after tissue biopsy	X Prior to initiating new systemic anti-tumor treatment AND no more than 8 weeks after tissue biopsy only in cases where a biopsy was performed

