4.2 Processing of Samples and Data Management

The Genomic Health staff involved in the processing of liquid biopsy samples will remain blinded to the central assessment of FPE tissue, Pathology and Clinical data. The laboratory performing central assessment of FPE tissue will be blinded to the results of the liquid biopsy. The liquid biopsy, central FPE tissue assessment, Pathology and Clinical data will be independently processed and reviewed for quality. Once all data QC review and reconciliation are completed and data are locked, Genomic Health Data Management will merge the liquid biopsy, FPE tissue assessment, Pathology and Clinical data and prepare the SAS analysis dataset, following standard Genomic Health procedures. There will be only one, unique Specimen Identifier, and this number will not provide Genomic Health staff a direct link to private patient information. The direct link to private patient information is maintained and secured by study sites and Genomic Health will have no access to this information.

Please see section 8.6 for additional information regarding the planned Interim Analysis.

CONFIDENTIAL – PROPRIETARY PROPERTY OF GENOMIC HEALTH, INC.

Study Protocol

Sample specimens will not be used to develop genetic lines or nucleic acid banks. Archived samples and/or left over specimens may be used for quality control and/or for exploratory analysis of test result concordance specific to relevant cancer gene alterations that are not currently included in the Genomic Health mutation panel.

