5. STUDY POPULATION

Initially, 200 patients will be enrolled regardless of genomic alteration status in tumor tissue (First Enrollment Phase). This will be followed by a Second Enrollment Phase including approximately 39 patients with clinically relevant alterations in EGFR and 21 patients with alterations in ALK (EML4-ALK fusions) (as assessed in tumor tissue). In addition, 50 patients progressing on erlotinib, gefitinib, or afatinib will be included across the enrollment phases (see Table 2 and Figure 1).

Participants may be included in the study only if they meet all the criteria listed below in Section 5.1 and if they are not excluded by any of the criteria listed below in section 5.2.

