7.5 Collection, and Processing of Pathology Samples

Enrolled subjects will have previously collected pathology tissue samples that will be utilized for the tissue-based sequencing if sufficient tumor material for analysis is available (as defined in section 4.1) and if patient approves of sending the material for analysis.

Local assessment of tumor tissue samples will be performed at each participating institution as per their clinical standard of care practices and results from the local assessment of genomic alteration status will be used. Each site will need to provide a single H&E slide to Genomic Health for an independent pathology review.

Genomic Health will receive and inspect the H&E slides according to approved internal receiving protocols. The received samples will be accessioned and quality inspected. Genomic Health standard histopathology assessments will be made from the single H&E slide of each FPE tumor tissue specimen by a Genomic Health designated pathologist(s) and will include: presence of tumor (adequate quantity).

Additional pathology measures will be obtained from the tissue biopsy pathology and mutation reports and entered into the electronic data capture system by the clinical site personnel.

Any residual DNA remaining after the conclusion of the study may be banked for future research. Tissue blocks or slides not used for analysis will be returned to the ordering physician but residual DNA will be stored by GHI. Future use will be explained in the ICF where the subject may elect to not approve banking their left over samples. All remaining samples or specimens will be de-identified and stored in an appropriate storage environment at Genomic Health. De-identified data associated with the banked left over samples will be stored in a secure Genomic Health database and will not be traceable to any identifiable protected health information.

CONFIDENTIAL – PROPRIETARY PROPERTY OF GENOMIC HEALTH, INC.

Study Protocol

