8.2 Analysis Populations

Statistical analyses will involve samples from patients with stage IV non squamous NSCLC. Samples that are not collected according to the sample preparation instructions, fail pathology review, fail to meet pre-specified analytical quality control metrics as defined by the Genomic Health LBMP's standard operating procedures, or fail to meet pre-specified quality control specification for the FPE assessment will be considered non-evaluable and will not be included in the analyses described in this section. Approximately 20% of enrolled patients are expected to have non-evaluable samples and thus results from approximately 248 evaluable patients are expected to be included in the analyses.

CONFIDENTIAL – PROPRIETARY PROPERTY OF GENOMIC HEALTH, INC.

Study Protocol

The primary analysis will be based on patients with non squamous NSCLC with evaluable plasma and tissue samples and reportable results from both the Genomic Health liquid biopsy test and tumor tissue assessments. The results of the central tissue assessments will be used when available. In patients without central CLIA laboratory results, local assessments of genomic alterations in tissue will be utilized. Exploratory analyses will include patients with evaluable samples from the Genomic Health liquid biopsy test and time to progression and available assessment of best response to therapy initiated after the liquid biopsy test.

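### Does the central-first tissue rule wrongly drop Second Enrollment Phase EGFR patients whose central result is negative?

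*Combined protocol and SAP*

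**What the plan says.** The reference rule appears twice in agreement. Section 8.2 says "The results of the central tissue assessments will be used when available" and turns to local results only for patients without a central CLIA result. The synopsis says "The results of the central tissue assessments will be used in analysis where available", with the same fallback.

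Sections 4, 4.1 and 7.5 describe routine testing at the sites and each add that "results from the local assessment of genomic alteration status will be used", without mentioning central priority. Section 4.2 nevertheless assumes a central assessment: "The laboratory performing central assessment of FPE tissue will be blinded to the results of the liquid biopsy". Section 6.4 does likewise.

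Section 7.5 makes tissue sequencing depend on material, "if sufficient tumor material for analysis is available (as defined in section 4.1"), and on patient approval. Section 4.1 contains no such definition.

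Table 2 describes the Second Enrollment Phase as "Approximate number of patients enrolled based on known gene alterations of interest", and section 5 puts it at "approximately 39 patients with clinically relevant alterations in EGFR" plus 21 with ALK. No section names the test that makes an alteration known. Table 3 requires a "Local mutation report", while sections 9 and 12.2 show that independent CLIA sequencing results also reach the site and the physician.

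In section 8.3, Table 4A (PPA) takes patients with EGFR detected in tissue. Table 4B (NPA) takes only patients enrolled regardless of alteration status. Section 8.4 repeats the concordance analyses in the subset with central results.

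**The concern.** Two things look wrong. First, three sections point to the local result and two to the central result, so the comparator for the primary estimate seems unsettled.

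Second, following section 8.2 creates a patient with no place. Someone recruited to enlarge the EGFR-positive group, then found EGFR-negative centrally, fails the entry condition of Table 4A and is barred from Table 4B. The central subset analysis in section 8.4 uses the same tables and does not bring that patient back. Section 8.3 explains why Second Enrollment Phase ALK patients are left out of NPA but is silent on this EGFR patient, and no count is planned.

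If local results qualify patients, centrally tested patients enrolled for EGFR enter PPA only when positive on two tissue tests, while centrally tested First Enrollment Phase patients enter on the central result alone. The pooled PPA would then mix two selection rules, with the larger share of its positives coming from the stricter one.

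**Working it through.** **Placement under section 8.2**

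| Enrollment | EGFR on the reference result | Table |
|---|---|---|
| First phase | positive | 4A |
| First phase | negative | 4B |
| Second phase, for EGFR | positive | 4A |
| Second phase, for EGFR | negative | neither |
| Second phase, for ALK | negative | neither (explained in 8.3) |

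The fourth row exists only if a non-central result qualified the patient and a central result was later negative. If the central result qualifies, the row is empty.

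**The plan's own figures reproduce.** Evaluable concordance patients: 260 × 0.8 = 208, as in section 8.7. Clopper-Pearson lower bound at 40/50: 0.663, against 0.66 in Table 5. Evaluable EGFR-positives on the same 20% loss: 30 × 0.8 = 24 in the first phase, 39 × 0.8 = 31.2 in the second, 69 × 0.8 = 55.2 together.

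**Effect of one patient.** Start from 44/55 = 80.0%. Leaving out a plasma-negative patient gives 44/54 = 81.5% (+1.5 points). Leaving out a plasma-positive one gives 43/54 = 79.6% (−0.4). The direction relative to an all-local reference is therefore open.

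**Model of unequal selection.** Only the prevalence of 15% comes from the documents (Table 2). Assumed: local results qualify; plasma detection is 80% in true positives; both tissue tests have sensitivity se and specificity sp with independent errors; a proportion pf of tissue false positives is plasma-positive; a share A of patients has a central result.

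- First-phase PPA = [0.15·se·0.80 + 0.85·(1−sp)·pf] / [0.15·se + 0.85·(1−sp)]
- PPV = 0.15·se / [0.15·se + 0.85·(1−sp)]
- Second phase, share kept and truly positive = PPV·(A·se + 1−A)
- Second phase, share kept and falsely positive = (1−PPV)·(A·(1−sp) + 1−A)

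Example with se 0.95, sp 0.99, pf 0.01, A = 1:

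- First phase: (0.1425 × 0.80 + 0.0085 × 0.01) / 0.151 = 75.6%, from 160 × 0.151 = 24.2 positives.
- PPV = 0.1425 / 0.151 = 0.944. Kept true = 0.944 × 0.95 = 0.897. Kept false = 0.056 × 0.01 = 0.001.
- Second phase: 31.2 × 0.897 = 28.0 kept (true plus false), so 3.2 drop out.
- Pooled PPA = 77.9%, which is 2.4 points above the first phase and nearer the assumed 80%.

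Pooled minus first-phase PPA, in points, at se 0.95 and sp 0.99:

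| Plasma positivity in tissue false positives | A = 10% | 25% | 50% | 100% |
|---|---|---|---|---|
| 1% | +0.2 | +0.6 | +1.1 | +2.4 |
| 40% | +0.1 | +0.3 | +0.6 | +1.2 |
| 80% | 0 | 0 | 0 | 0 |
| 90% | −0.03 | −0.07 | −0.14 | −0.30 |

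The corresponding dropouts among 31.2 patients are 0.3, 0.8, 1.6 and 3.2.

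The largest shift over se 90–99%, sp 98–100% and pf 1–80% is +4.4 points with 6.2 dropouts. It needs se 0.90, sp 0.98, pf 0.01, central results for everyone and independent errors. At 50% availability the same corner gives +2.1 points and 3.1 patients. With full availability and an assumed error correlation of 0.5 between the two tests, it gives +2.1 points, and the example above falls from +2.4 to +1.1.

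**Scale.** The 95% Clopper-Pearson interval is 0.67 to 0.90 at 44/55. For first-phase PPA alone, at 19/24, it is 0.58 to 0.93.

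**The case for a change.** The best case for a change is that PPA is the primary estimate and its denominator should be beyond doubt. The local reading is plausible: Table 3 asks for a local report, and section 7.5 reads as if central sequencing follows enrollment. A few discordant patients can matter. With three of them, all plasma-negative, central-first gives 42/52 = 80.8% and an all-local reference gives 42/55 = 76.4%. If all three are plasma-positive, the all-local figure is 45/55 = 81.8%. ALK agreement follows the same tables, with 21 of 31 patients from the Second Enrollment Phase. Aligning the text and adding a table would cost little.

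The textual part stands: three sections omit central priority, the reference to section 4.1 leads nowhere, and the qualifying test is unnamed. The inference to a flawed estimate does not. The four-point difference compares two choices of reference, and section 8.2 has already chosen between them. Keeping a centrally negative patient in Table 4A would abandon that choice for precisely the patients in whom it matters.

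The extra analyses would also say little. PPA by phase cannot resolve a difference of about two points when the first-phase interval is 0.58 to 0.93, and the phases may differ in their mix of newly diagnosed and progressing patients. An all-local PPA would change the reference for first-phase patients too. A count of discordant patients would inform the reader, but it alters no estimate, and the analyst will have both results in hand.

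**Conclusion.** No change is needed. Section 8.2 is the specific rule for the primary analysis and the synopsis repeats it. The local-results sentences in sections 4, 4.1 and 7.5 can be read with it, since local results are indeed used wherever no central result exists. Once the reference is fixed, the patient's absence from both tables follows from the definitions: PPA conditions on a positive reference, and admitting patients recruited for a known alteration to NPA would defeat the restriction in section 8.3.

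The issue also needs two conditions that the documents leave open: a non-central qualifying result and a later negative central one. Its size is unknown because no discordance rate, central availability or plasma detection rate in discordant patients is given. In the model most settings give 0 to about 2 points, toward the assumed detection rate and well inside 0.67 to 0.90. The +4.4-point figure is an extreme corner, and no bias away from the truth is shown. The study is descriptive with no hypothesis test, so no decision turns on it.

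What is left is clerical wording and a detail that analysts can settle from the definitions. Section 8.1 defers detailed methods to a separate Statistical Analysis Plan, whose text is not part of the document and which may already cover discordant results.

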7.3 Clinical Assessment and Data Capture

Demographic and clinical data on each participant will be collected at the enrollment visit. All clinical and demographic variables will be obtained from the clinical sites through a validated electronic data capture (EDC) system. The demographic variables will include age and gender. The clinical variables will include diagnosis, stage, histology of the tumor, marker status of primary tumor/metastatic site if available, site(s) of metastatic disease and treatment (prior targeted therapy, last therapy given prior to study enrollment and therapy after liquid biopsy). Additionally, dates of diagnosis, surgery, treatment, metastatic tissue biopsy, liquid biopsy, and of documented disease progression (defined as first objective evidence of progression (increasing tumor size or new lesions) by clinical examination or imaging) after liquid biopsy will be collected, when applicable. The clinical site will provide follow up clinical information including treatment given after liquid biopsy, best response to this treatment (complete response, partial response, stable disease or progressive disease) and date of progression or, at 12 months after liquid biopsy, if still on treatment without progression at that time. Follow up should also be completed upon patient death should that occur prior to first progression or 12 months after liquid biopsy. Genomic Health or its designee will provide the clinical sites with access to a validated EDC system for electronic case report form (eCRF) documentation. The eCRFs will be completed for each study participant through chart abstraction. It is the investigator's responsibility to ensure the accuracy, completeness, and timeliness of the data reported in the participant's eCRF. Source documentation and/or objective evidence supporting the eCRF data should indicate the participant's inclusion in the study and should document the dates and details of study procedures, adverse events, and participant status. The

CONFIDENTIAL – PROPRIETARY PROPERTY OF GENOMIC HEALTH, INC.

Study Protocol

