8. STATISTICAL METHODS

8.1 General Methods

This section provides a general description of the statistical analysis methods. A detailed description of the analysis methods will be provided in the Statistical Analysis Plan, that will be developed blinded to any analytical test results (i.e. from the liquid biopsy tests and tumor tissue assessments) and finalized prior to the data lock for the interim analysis.

This is a descriptive study to characterize the concordance between the results of the Genomic Health LBMP based on plasma and genomic assessment of the tumor tissue. Both the liquid biopsy and the tumor tissue assessments will report the status of the investigated alterations in a binary manner as detected or not detected. No formal hypothesis testing is planned. Unless otherwise stated, two-sided 95% Clopper-Pearson confidence intervals will be reported²⁸.

The analysis of a single tumor biopsy cannot yield a reference standard for a liquid biopsy assessment due to tumor multifocality and intra- and inter-tumor heterogeneity in stage IV disease. As described in the FDA Statistical Guidance on Reporting Results from Studies Evaluating Diagnostic Tests (2007), when a new test is evaluated by comparison to a non-reference standard, it is not possible to directly calculate unbiased estimates of sensitivity and specificity. Therefore, due to lack of reference standard for analysis of liquid biopsies, it would not be appropriate to describe the comparative results of the study in terms of sensitivity and specificity. Instead, we will characterize the concordance in terms of positive percent agreement (PPA) and negative percent agreement (NPA) as presented in section 8.3, Table 4.

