8.5 Exploratory Analyses

We will examine the association between the presence of alterations in plasma or tissue and endpoints such as time to progression and response to first therapy initiated after liquid biopsy.

Time to progression is defined as time from first initiated therapy (after liquid biopsy) to progression as documented by imaging or clinical evaluation. Progression identified at the time of death will be considered an event. Patients still on therapy one year after the liquid biopsy assessment will be censored. We will use Cox proportional hazards regression models and Kaplan-Meier analyses and will consider non-linear techniques, including smoothing splines. Subset analyses based on alteration status in tissue and plasma may be conducted.

CONFIDENTIAL – PROPRIETARY PROPERTY OF GENOMIC HEALTH, INC.

Study Protocol

Response is defined as best response to therapy initiated after liquid biopsy (complete response, partial response, stable disease or progressive disease). We will use logistic regression models and will consider non-linear techniques, including smoothing splines.

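### Read literally, Section 8.2 admits patients to the time-to-progression analysis only if a best response was also recorded, so some early deaths and losses can be removed for a post-baseline reason

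*Combined protocol and SAP*

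**What the plan says.** The population sentence for the exploratory work is in Section 8.2: "Exploratory analyses will include patients with evaluable samples from the Genomic Health liquid biopsy test and time to progression and available assessment of best response". It joins three conditions with the word and: an evaluable plasma result, a TTP and a best response.

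Section 8.5 states the aim, "We will examine the association between the presence of alterations in plasma or tissue and endpoints such as time to progression and response", and defines the two endpoints separately. For TTP it says "Time to progression is defined as time from first initiated therapy (after liquid biopsy) to progression as documented by imaging or clinical evaluation". Its event and censoring rules are "Progression identified at the time of death will be considered an event" and "Patients still on therapy one year after the liquid biopsy assessment will be censored". It names no separate patient set for TTP and gives no rule for a death at which progression was not identified.

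Section 7.3 covers data capture. Best response has four categories (complete response, partial response, stable disease, progressive disease), with no category for a patient who was not evaluable. Progression may be established by clinical examination or imaging. On deaths, "Follow up should also be completed upon patient death should that occur prior to first progression or 12 months after liquid biopsy". Data come from chart abstraction, and Section 4.1 provides for no further study visits after the blood draw.

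**The concern.** Best response is observed after therapy starts. Making it an entry condition for a time-to-event analysis selects patients on a post-baseline outcome. A patient with stage IV disease who starts therapy and dies before any response is written in the chart may have a complete follow-up record under Section 7.3 and still be excluded by Section 8.2. The same condition takes that patient out of the denominator for response.

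Objective 6.3.1 relates alterations to TTP and response. If blank responses are commoner in one alteration group than in another, the comparison is made between groups that have been selected differently. Section 8.2's allowance for loss (about 20%) covers non-evaluable samples only and does not reflect missing response. Section 4.1 foresees outcome data for the interim analysis, Section 8.6 allows an abstract from that analysis, and Section 15 anticipates publication, so these results may be seen outside the sponsor.

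**Working it through.** **1. The plan's own figure.** Section 8.2 expects about 248 evaluable patients: 310 × (1 − 0.20) = 248, which reproduces. The documents give no number for the exploratory set, no TTP assumption and no expected rate of missing response. The size of any bias therefore cannot be computed from them, and everything from step 3 on is illustration.

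**2. Who is exposed (Sections 7.3, 8.2 and 8.5 read together).**

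| Patient after starting therapy | TTP under 8.5 | Best response under 7.3 | In the literal 8.2 set? |
|---|---|---|---|
| Early progression, clinical or imaging | Event | Progressive disease can be recorded | Yes, if recorded |
| Early death, progression identified | Event | Progressive disease or blank; no rule | Only if recorded |
| Early death, progression not identified | No stated rule | Probably blank; no rule | No, if blank |
| Lost before any assessment | No stated rule | Blank | No |

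The exposed patients are mainly early deaths and losses with a blank response field.

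**3. If the excluded patients would have been events.** Assume exponential TTP with true median m = 6.0 months, and a first assessment at 8 weeks (1.84 months). The share with an event before then is F = 1 − 2^(−1.84/6) = 0.19. If a fraction q of these have no response, d = qF of all patients are dropped. The apparent median solves S(t)/(1 − d) = 0.5, so t = m × [1 + log2(1/(1 − d))].

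| q | d | Apparent median (months) |
|---|---|---|
| 25% | 4.8% | 6.4 |
| 50% | 9.6% | 6.9 |
| 75% | 14% | 7.3 |

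A second model gives the same direction. Let a share of all patients have an event spread uniformly over 0 to 2 months and no recorded response, and let the rest have a 6-month median. Simulated Kaplan-Meier medians (400,000 patients, censoring at 12 months), with these patients kept versus excluded, are 5.8 vs 6.0 (2% share), 5.6 vs 6.0 (5%), 5.1 vs 6.0 (10%) and 4.6 vs 6.0 (15%). At 248 patients these shares are about 5, 12, 25 and 37 people. If half of them have progressive disease recorded and stay in, the set left by the exclusion at the 10% share has a median of 5.5, against 5.1 with everyone kept.

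**4. If the excluded patients would have been censored.** In the second model, treating the early cases as censored deaths gives medians of 6.0 to 6.2 months when they are kept, against 6.0 when excluded. Exclusion then overstates nothing.

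**5. The association.** Take true medians of 5 and 10 months in two groups, the exponential model of step 3 and q = 50%. The shares dropped are 11% and 6%, and the medians become 5.9 and 10.9. Events per person-month over 12 months become 0.6980/5.748 = 0.121 and 0.5049/8.093 = 0.0624, so the rate ratio moves from 0.50 to 0.0624/0.121 = 0.51.

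The direction is not fixed. In Cox models on simulated data (20,000 per group, hazard ratio 0.60 among patients without an early event):

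| Early share, marker-positive / marker-negative | HR, early events kept | HR, excluded |
|---|---|---|
| 10% / 10% | 0.65 | 0.60 |
| 15% / 5% | 0.73 | 0.60 |
| 5% / 15% | 0.55 | 0.60 |

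**The case against.** The strongest reply is that the sentence in 8.2 can be read endpoint by endpoint: TTP data for the TTP analysis and response data for the response analysis. Section 8.5 treats the endpoints separately, and Section 8.1 describes Section 8 as general and leaves detail to a Statistical Analysis Plan. This reading is possible. However, the primary-analysis sentence in 8.2 uses the same conjunction cumulatively, and nothing in 8.5 overrides the joint condition. Two programmers could build different datasets, so the sentence needs rewriting on either reading.

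A second reply is that a TTP event is documented progression, which is what supports an entry of progressive disease. Patients with an event would then seldom have a blank response, and the fractions dropped in step 3 would be too high. This largely stands. It narrows the exposed group to early deaths and losses, and the documents support no particular value of q. It does not remove the risk, because no rule says what is entered for a patient who dies unassessed.

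A reader might go further and infer that all patients who deteriorate early drop out, that TTP is therefore overstated, and that the contrast between alteration groups shrinks. The documents do not support this. Clinical progression counts as progression, progressive disease is a response category, deaths without identified progression are not stated TTP events, and step 5 shows the hazard ratio moving either way.

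**Conclusion.** The point holds as a defect in the definition of the analysis set. Followed as written, 8.2 conditions TTP on a post-baseline response assessment, and 8.5 does not undo it. Mainly early deaths and losses with a blank response field are affected.

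The size is unknown from the documents. Under the stated assumptions the median is lengthened from 6.0 to between 6.4 and 7.3 months if the removed patients would have been events, and by about nothing if they would have been censored. Bias in the association has no fixed direction and may be small; a rate ratio moving from 0.50 to 0.51 is one example. These figures rest on assumed medians, an assumed 8-week first assessment and assumed fractions unassessed.

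Severity is low. The objective is exploratory, Section 8.1 says "No formal hypothesis testing is planned", and the primary and secondary concordance analyses are untouched.

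**What to change.** Replace the exploratory sentence in 8.2 with two sets, and carry them into the Statistical Analysis Plan:

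- **TTP set:** all patients with an evaluable plasma result who start a therapy after the liquid biopsy, whether or not a best response was recorded. Add to 8.5 an analysis rule for death without documented progression; without it, restoring these patients leaves their contribution undefined.
- **Response set:** the same patients. Those unassessed because of early death or clinical progression stay in the denominator as non-responders, with a supplementary result in assessed patients only. Counting them as non-responders is a convention, and the supplementary result shows how much depends on it.
- **Reporting:** the number with missing best response, by alteration status, so that a reader can judge whether the loss is differential.

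The cost is wording in 8.2, 8.5 and the Statistical Analysis Plan. Section 7.3 already collects the data. Reported TTP and the response proportion may become slightly less favourable.
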